8.4.1 Adverse Event Reporting

AEs will be reported in accordance with federal law and IRB requirements. Reporting procedures vary depending on the severity of the AE. All non-reportable AEs and other Ups not related to study activities and that do not increase the risk of harm or result in harm to participants will be reported to the IRB at the time of continuing review.

8.4.2 Serious Adverse Event Reporting

SAEs considered at least possibly related to the study procedures will be reported to the IRB within 48 hours of discovery by the PI. The PI will distinguish SAEs from AEs and provide attributions (severity, relationship, expectedness).

8.4.3 Unanticipated Problem Reporting

Incidents or events that meet the OHRP criteria for UPs require the creation and completion of an UP report form. It is the site investigator's responsibility to report UPs to their IRB. The UP report will include the following information:

- Protocol identifying information: protocol title and number, PI's name, and the IRB project number;
- A detailed description of the event, incident, experience, or outcome;
- An explanation of the basis for determining that the event, incident, experience, or outcome represents an UP;
- A description of any changes to the protocol or other corrective actions that have been taken or are proposed in response to the UP.

To satisfy the requirement for prompt reporting, UPs will be reported using the following timeline:

- UPs that are SAEs will be reported to the IRB within 48 hours of the investigator or other qualified designee becoming aware of the event.
- Any other UP will be reported to the IRB within 5 working days of the investigator or other qualified designee becoming aware of the problem.

8.5 Study Halting Rules

The medical monitor will convene to determine whether the study should be halted after three severe AEs with probable relationship to the study procedures are discovered. The PI or qualified designee will inform the medical monitor within 24 hours of this occurrence, cease screening and enrollment of new participants, and will provide the medical monitor with a list of AEs. The medical monitor will convene an ad hoc meeting by teleconference or in writing as soon as possible and will provide recommendations for proceeding with the study to the PI. If the medical monitor finds it is likely that the study procedures

contributed to negative outcomes, they will consider solutions including protocol modifications or potentially terminating the study.

8.6 Safety Oversight

It is the responsibility of the Principal Investigator to oversee the safety of the study at his/her site. This safety monitoring will include careful assessment and appropriate reporting of adverse events as noted above, as well as the construction and implementation of a site data and safety-monitoring plan. Medical monitoring will include a regular assessment of the number and type of serious adverse events. A summary of adverse events, deviations, and findings by the medical monitor will be submitted to the IRB as part of an annual progress report with each Continuing Review submission.

9 Clinical Monitoring

Clinical site monitoring is conducted to ensure that the rights and well-being of human subjects are protected, that the reported trial data are accurate, complete, and verifiable, and that the conduct of the trial is in compliance with the currently approved protocol/amendment(s), with GCP, and with applicable regulatory requirement(s). Senior Site Staff will be responsible for local quality assurance, will verify that the study procedures are properly followed, and will ensure that site staff are trained and able to conduct the protocol appropriately. If the Senior Site Staff's review of study documentation indicates that additional training of study personnel is needed, or that other corrective action is required, arrangements will be made via the PI. Senior Site Staff will review data for completeness, accuracy, and fidelity to the protocol.

10 Statistical Considerations

10.1 Statistical and Analytical Plans (SAP)

This pilot study is not formally powered to assess effect statistically. We will: demonstrate the NYU team can successfully recruit, enroll, and complete the protocol as proof of concept and collect high-quality analyzable data; and assess clinically meaningful improvement on primary outcome measures (AISRS and ASRS/BRIEF-A) as demonstrated by effect size of change.

As this is a pilot study and the full estimation of the potential magnitude of the effect is not known, we are planning an interim analysis after completion of approximately 10 patients with treatment data. This interim analysis examine the magnitude of clinical effects on clinical measures of AISRS expanded AISRS subsets (clinician symptom measure), ASRS (self-report symptom measure), BRIEF (self-report measure of executive function) and CGI (measure of impairment) via examination for means, SDs and magnitude of effect. Safety data will also be examined.

ADHD Rationale

In this study, approximately 30 subjects will be phone prescreened, which will give us at least 30 participants coming in for screening and consenting for participation. Up to 30 patients will be enrolled/consented to be sure that 15 evaluable/assigned

CONFIDENTIAL

patients reach the end of PRISM Intervention. We expect some of the subjects to screen fail either during the telephone phone screen or during the hybrid remote visit. Screen failures can occur during the MINI (psychiatric interview), ACDS (ADHD diagnosis interview) or upon discretion of the principal investigator. Subjects are also given the opportunity to continuously decide participation throughout the study. Subjects can opt out of the study at any time.

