Brief Summary	This is a single-arm, open-label feasibility study. A maximum of 30 participants will be enrolled. 15 participants will be assigned and will undergo a novel neurofeedback intervention, targeting down-regulation of deep limbic structures, specifically the amygdalae. Participants will complete 15 neurofeedback sessions delivered twice weekly over 8 consecutive weeks. The intervention will be delivered via the PRISM platform.	
Phase	Pilot	
Objectives	1)Train the NYU team on the electric finger print electroencephalography neurofeedback (EFP-EEG-NF) technology and provide them with hands-on experience; 2) Assess participants' ability to learn the feedback paradigm (i.e. control the EFP-EEG-NF signal; time to achieve learning; assess learning curves); 3) Explore preliminary results assessing emotional dysregulation measured on subsets of AISRS and BRIEF-A.	
Methodology	Open label	
Endpoint	Primary: Demonstrate the NYU team can successfully recruit, enroll, and complete the protocol as proof of concept and collect high-quality analyzable data; Secondary: Clinically meaningful improvement on primary outcome measures (AISRS and BRIEF-A) demonstrated by effect size of change.	
Study Duration	1 year	
Participant Duration	11 weeks	
Duration of IP administration	8 weeks	

Population	Adults ages 18-60 with a diagnosis of Attention Deficit/ and Hyperactivity Disorder-Adults (ADHD) who otherwise meet study inclusion and exclusion criteria.
Study Sites	New York University School of Medicine
Number of participants	30 participants expected to be enrolled; 15 expected to complete the study
Description of Study Agent/Procedure	Neurofeedback sessions will be delivered via the PRISM system. This is a non-significant risk device.
Reference Therapy	N/A
Key Procedures	Clinical evaluation, EFP-EEG-NF training, EFP-EEG-NF sessions, AE evaluation, and participant satisfaction measures.
Statistical Analysis	This is a pilot study and is not formally powered to assess effect statistically. See Statistical Explanation section

Page 9

1 Key Roles

[name], Principal -Investigator

Department of Psychiatry NYU Grossman School of Medicine [name] [contact] [contact]

[name], Co-Investigator Department of Psychiatry NYU Grossman School of Medicine [name] [contact] [contact]

[name] Department of Psychiatry NYU Grossman School of Medicine [name] [contact] [contact]

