4.2.2 Secondary Study Endpoints

30% meaningful improvement on primary outcome measures (AISRS and ASRS/BRIEF-A) demonstrated by effect size of change scores.

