5.6 Total Number of Participants and Sites

Recruitment will end when approximately 30 participants are enrolled. It is expected that approximately 30 participants will be enrolled in order to produce 15 evaluable participants.

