5.7.2 Handling of Participant Withdrawals or Termination

Every effort will be made to continue follow-up of withdrawn or terminated participants or participants who discontinue the study intervention but remain in the study for follow-up. If a participant is lost to follow-up, the study team will attempt contact up to 15 times via phone or email to capture adverse events (AEs), serious adverse events (SAEs), and unanticipated problems (Ups). Participants who withdraw or discontinue early will not be replaced.

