10.2 Sample Size

We will consent approximately 30 participants to meet our goal of 15 completers.

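### An effect size of change is to demonstrate meaningful improvement, but it is undefined and has no interval; with 15 completers an observed 0.5 SD of change has a 95% CI that includes zero

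*Combined protocol and SAP*

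**What the plan says.** Section 10.1 opens with "This pilot study is not formally powered to assess effect statistically". The same paragraph then undertakes to "assess clinically meaningful improvement on primary outcome measures (AISRS and ASRS/BRIEF-A) as demonstrated by effect size of change".

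The endpoint is worded differently in two other places. The Protocol Summary gives "Clinically meaningful improvement on primary outcome measures (AISRS and BRIEF-A) demonstrated by effect size of change". Section 4.2.2 gives "30% meaningful improvement on primary outcome measures (AISRS and ASRS/BRIEF-A) demonstrated by effect size of change scores". Only 4.2.2 has the 30% figure, and the Summary omits the ASRS.

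For the interim look after about 10 patients, section 10.1 says the clinical measures will be examined "via examination for means, SDs and magnitude of effect". That list belongs to the interim; no list of statistics is given for the final analysis.

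On numbers, section 10.2 says "We will consent approximately 30 participants to meet our goal of 15 completers", and section 5.7.2 says "Participants who withdraw or discontinue early will not be replaced".

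No section mentions a confidence interval, standard error or test for any outcome. None states the divisor of the effect size, the visits that define change, or what value would count as meaningful. The scales are rated at screening, baseline, weekly during training and at Week 11 (sections 7.1 and 7.2), so several definitions of change are possible.

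**The concern.** A study that says it is not powered can still give a useful estimate, but it cannot let a point value carry a demonstration. As written, an effect size computed from 15 people could be reported as demonstrated improvement even when the data are compatible with no change.

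The undefined effect size adds to this. The same data give different values depending on the SD used and the visit chosen, and both could be settled after the results are known. The 30% figure could have anchored the claim. However, 4.2.2 does not say whether it is a mean percentage change or a per-patient response, nor how an effect size would show it.

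What is at stake is how the secondary endpoint is reported. The feasibility endpoint in section 4.2.1 is not affected.

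**Working it through.** **The plan's own figure.** The only sample-size statement is 30 consented for 15 completers. Since 15 / (1 - 0.5) = 30, this implies 50% loss, which is inferred and not stated. No alpha, power, effect size, SD or precision target is given, so 15 cannot be derived as a statistical number.

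**Inputs from the documents.** n = 15 (10.2, 5.6); interim n of about 10 (10.1); single arm, hence within-patient change (4.1); AISRS entry minima of 28 without and 22 with ADHD medication (5.1); 30% (4.2.2).

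**Assumptions.** Two-sided 95% level; medium effect = 0.5; SD of AISRS change 6 to 12 points; pre-post correlation r = 0.3 to 0.8; equal SDs at the two visits.

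**Step 1: interval at n = 15.** Let d = mean change / SD of change. For d = 0.5, t = d × √n = 0.5 × 3.873 = 1.94 on 14 df, two-sided p = 0.073. The exact noncentral-t 95% interval is -0.05 to 1.03. The ordinary t interval has half-width 2.145 / 3.873 = 0.554, giving -0.05 to 1.05. The observed d must reach about 0.56 before the interval excludes zero; an observed 0.5 would need n = 18.

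| Observed d | 95% CI, n = 15 | 95% CI, n = 10 |
|---|---|---|
| 0.2 | -0.32 to 0.71 | -0.43 to 0.82 |
| 0.4 | -0.13 to 0.92 | -0.26 to 1.04 |
| 0.5 | -0.05 to 1.03 | -0.17 to 1.15 |
| 0.6 | 0.04 to 1.14 | -0.09 to 1.26 |
| 0.7 | 0.12 to 1.26 | -0.01 to 1.38 |

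**Step 2: confidence level.** At d = 0.5 the 90% interval is 0.04 to 0.94 for n = 15, which excludes zero. For n = 10 it is -0.07 to 1.04, which does not.

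**Step 3: divisor.** With equal SDs, SD of change = baseline SD × √(2(1 - r)). An effect of 0.5 in baseline-SD units is therefore 0.5 / √(2(1 - r)) in SD-of-change units. At n = 15, back on the baseline-SD scale:

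- r = 0.3: 0.5 / 1.183 = 0.42; 95% CI -0.13 to 1.12
- r = 0.5: 0.5 / 1.000 = 0.50; 95% CI -0.05 to 1.03
- r = 0.7: 0.5 / 0.775 = 0.65; 95% CI 0.06 to 0.93
- r = 0.8: 0.5 / 0.632 = 0.79; 95% CI 0.12 to 0.86

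The switch is at r = 1 - (0.5 / 0.554)² / 2, about 0.59.

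**Step 4: small-sample correction.** The factor is 1 - 3/(4 × 14 - 1) = 0.945 at n = 15, so 0.5 becomes 0.47. It is 1 - 3/(4 × 9 - 1) = 0.914 at n = 10, so 0.5 becomes 0.46.

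**Step 5: the 30% figure.** At the entry minima, 30% is 0.3 × 28 = 8.4 or 0.3 × 22 = 6.6 points. With an SD of change of 6 to 12, that is d = 0.70 to 1.40 or 0.55 to 1.10. Conversely, d = 0.5 is 3 to 6 points, or 11% to 21% of 28 and 14% to 27% of 22. The two criteria are not interchangeable, and at these baselines a d of 0.5 falls short of 30% throughout the assumed range.

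**Step 6: what a responder proportion would give.** For illustration, 8 of 15 is 53%, exact 95% CI 27% to 79%.

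**The case against.** The strongest reply is that this is a declared pilot with a feasibility primary endpoint (4.2.1) and a clinical aim only to explore preliminary results (3.1). Precision is then not the purpose, and 4.2.2 does supply a clinical benchmark. That excuses the lack of a power calculation or test. It does not excuse saying that improvement is demonstrated by a number with no stated uncertainty, and the benchmark is not connected to that number.

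It can also be said that readers could work out an interval from means, SDs and n. SDs are promised only at the interim, and not specifically SDs of change. Visit-level SDs without the pre-post correlation do not give an interval for change.

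The objection that the d = 0.5 result is borderline stands. It depends on the 95% level and on dividing by the SD of change.

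Three stronger readings are tempting but not supported:

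- **A high false-positive rate across several scales.** No section sets d = 0.3 or 0.5 as success or counts a result on any one scale, so such a rate would belong to a rule the plan does not contain.
- **Means, SDs and magnitude as the whole analysis.** Section 10.1 lists them for the interim only.
- **Use of the observed effect to size later trials.** Section 2.3 links later trials to recruitment, completion and data quality; no section plans that use.

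**Conclusion.** The point holds as a fault in how the secondary endpoint is to be concluded, not in the size of the study. The plan attaches a claim of demonstration to an undefined effect size with no interval. With 15 completers, an observed 0.5 SD of change has a 95% CI of -0.05 to 1.03. With about 10 at the interim it is -0.17 to 1.15.

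This rests on an assumed medium effect of 0.5, a two-sided 95% level and the SD of change as divisor. At n = 15, a 90% level or baseline-SD units with r above about 0.59 would exclude zero. That a conclusion can turn on choices the plan leaves open is part of the fault. Because withdrawals are not replaced, and section 4.1 caps enrolment at 15 where 5.6 and 10.1 speak of about 30, the analysed number may be below 15 and the interval wider.

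A reader might infer that an interval excluding zero would settle the matter. It would not: it would show change, which is not the same as clinically meaningful change. In a single-arm, open-label study it would not show an effect of the device either.

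**What to change.** In the Protocol Summary, section 4.2.2 and section 10.1:

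- Replace *demonstrated by* with *estimated by*, and name the same scales in all three places.
- Define the effect size: which SD is the divisor, and which visits define change (for example baseline to Week 11).
- For each named scale, report the mean change and the small-sample-corrected effect size, both with 95% CIs, at the interim as well as at the end.
- Report the proportion of participants with at least 30% improvement, with an exact 95% CI, so that the 30% figure has a stated meaning.
- State that, without a control arm, the estimates describe change and not a device effect.

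The cost is a few lines of SAP text and slightly more routine analysis, with no added patients, visits or data. The conclusion will look less favourable than a bare effect size would.

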10.1.1 Safety Review

See Section 5.6 Premature Termination or Suspension of Study and Section 8.5 Stopping Rules.

10.2 Sample Size

We will consent approximately 30 participants to meet our goal of 15 completers.

10.3 Measures to Minimize Bias

10.3.1 Enrollment/Randomization/Masking Procedures

Blinding, randomization, and masking are considered unnecessary for this pilot study. All subjects will undergo the same procedures.

11 Source Documents and Access to Source Data/Documents

Source data is all information, original records of clinical findings, observations, or other activities in a clinical trial necessary for the reconstruction and evaluation of the trial. Source data are contained in source documents. Examples of these original documents, and data records include: hospital records, clinical and office charts, laboratory notes, memoranda, subjects' diaries or evaluation checklists, pharmacy dispensing records, recorded data from automated instruments, copies or transcriptions certified after verification as being accurate and complete, microfiches, photographic negatives, microfilm or magnetic media, x-rays, subject files, and records kept at the pharmacy, at the laboratories, and at medico-technical departments involved in the clinical trial. It is acceptable to use CRFs as source documents. If this is the case, it should be stated in this section what data will be collected on CRFs and what data will be collected from other sources.

The study case report form (CRF) is the primary data collection instrument for the study. All data requested on the CRF must be recorded. All missing data must be explained. If a space on the CRF is left blank because the procedure was not done or the question was not asked, write "N/D". If the item is not applicable to the individual case, write "N/A". All entries should be printed legibly in black ink. If any entry error has been made, to correct such an error, draw a single straight line through the incorrect entry and enter the correct data above it. All such changes must be initialed and dated. DO NOT ERASE OR WHITE OUT ERRORS. For clarification of illegible or uncertain entries, print the clarification above the item, then initial and date it.

Access to study records will be limited to IRB-approved members of the study team. The investigator will permit study-related monitoring, audits, and inspections by the IRB/EC, the sponsor, government regulatory bodies, and University compliance and

CONFIDENTIAL

quality assurance groups of all study related documents (e.g. source documents, regulatory documents, data collection instruments, study data etc.). The investigator will ensure the capability for inspections of applicable study-related facilities (e.g. pharmacy, diagnostic laboratory, etc.).

Participation as an investigator in this study implies acceptance of potential inspection by government regulatory authorities and applicable University compliance and quality assurance offices.

12 Quality Assurance and Quality Control

QC procedures will be implemented beginning with the data entry system and data QC checks that will be run on the database will be generated. Any missing data or data anomalies will be communicated to the site(s) for clarification/resolution.

Following written SOPs, the monitors will verify that the clinical trial is conducted and data are generated, documented (recorded), and reported in compliance with the protocol, GCP, and the applicable regulatory requirements (e.g., Good Laboratory Practices (GLP), Good Manufacturing Practices (GMP)).

The investigational site will provide direct access to all trial related sites, source data/documents, and reports for the purpose of monitoring and auditing by the sponsor, and inspection by local and regulatory authorities.

13 Ethics/Protection of Human Subjects

13.1 Ethical Standard

The investigator will ensure that this study is conducted in full conformity with Regulations for the Protection of Human Subjects of Research codified in 45 CFR Part 46, 21 CFR Part 50, 21 CFR Part 56, and/or the ICH E6.

13.2 Institutional Review Board

The protocol, informed consent form(s), recruitment materials, and all participant materials will be submitted to the IRB for review and approval. Approval of both the protocol and the consent form must be obtained before any participant is enrolled. Any amendment to the protocol will require review and approval by the IRB before the changes are implemented to the study. All changes to the consent form will be IRB approved; a determination will be made regarding whether previously consented participants need to be re-consented.

13.3.1 Consent and Other Informational Documents Provided to Participants

Consent forms describing in detail the study procedures, potential risks, and potential benefits will be given to participants and written documentation of informed consent will be obtained prior to starting intervention. The following consent materials are submitted with this protocol:

- Request for Waiver of Authorization and Waiver of Documentation of Consent (Pre-Screen)
- Pre-Screen Consent Phone Script
- Informed Consent Form
- Informed Consent Quiz
- Audio/Video Release Form
- Health Release Form
- Covid 19 participation info sheet

Audio/Video Release Form: This form will be provided to participants and will include a description of the audio/video recording procedure, risks and benefits of the procedure, confidentiality, a statement that patients will be informed of any new findings affecting the risks or benefits of the study; a statement that participation is voluntary and that the patient may withdraw at any time; and information about whom to contact with questions or in case of emergency

Health Release Form: This form will be obtained to authorize release personal information in records from hospitals, clinics, or doctor's offices where participants have received care in the past. The form also authorizes the study team to speak with clinicians who have treated the patient for medical and/or psychiatric conditions but will not reveal the nature of the study without the patient's permission. The release will be only be utilized by the study team if necessary to determine study eligibility. Participants who do not authorize release may still participate in the study if there are no eligibility concerns. Participants who do not authorize release and for whom eligibility concerns have been raised will be assessed by the Principal Investigator and may be enrolled or withdrawn at his discretion.

